10.2.6 Analysis of Primary Safety Endpoint

For the composite primary safety endpoint, the proportion of subjects with device success and free from device- and/or procedure-related SAEs (per CEC adjudication) at 30 days, along with exact 95% confidence interval (CI), will be summarized. The summaries for each individual safety data point will also be provided.

10.2.7 Analysis of Clinical Endpoints

Definition of clinical endpoints are described in **Section 3.2**.

For composite endpoints, i.e., technical success, patient success, and device success, the number and percentage of subjects with success will be summarized. Descriptive statistics for components of each endpoint will also be provided.

For continuous variables (e.g., KCCQ scores and 6MWT distances), results will be summarized with the numbers of observations, means, standard deviations, minimums, maximums, and 95% confidence intervals. Change from baseline will be included using these same descriptive statistics.

For categorical variables such as mortality and NYHA classification, results will be summarized with subject counts and percentages/rates, and with 95% confidence intervals.

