3.2 Clinical Endpoints

The following clinical endpoints will be evaluated:

- Technical success evaluated upon exit from procedure room, defined as:
 - 1) Absence of procedural mortality; and
 - 2) Successful access, delivery and retrieval of the device delivery system; and
 - 3) Successful deployment and correct positioning of the intended device; and
 - 4) Freedom from emergency surgery or re-intervention related to the device or access procedure
- Patient Success evaluated at 1, 2, 3, 4, and 5 years post index procedure, defined as:
 - 1) Device Success (either optimal or acceptable); and
 - 2) Subject returned to the pre-procedural setting (e.g. home, assisted living facility); and
 - 3) No transcatheter or surgical re-interventions for mitral valvular disease (modified from MVARC guidelines); and
 - 4) Improvement from baseline symptoms (NYHA improvement by ≥ 1 Functional Classification); and
 - 5) Improvement from baseline in functional status (6MWD improvement by ≥ 50 meters); and
 - 6) Improvement from baseline in Quality of Life (KCCQ improvement by ≥ 10 points)
- Device Success as measured at 30 days and at all post-procedural intervals
- Freedom from all-cause mortality at 3 months, 6 months, 1 year, and then annually through 5 years post index procedure
- Distance walked on the 6MWT at baseline, 30 days, 3 months, 6 months, 1 year, and then annually through 5 years post index procedure (change from baseline to follow-up)
- KCCQ QoL scores at baseline, 30 days, 3 months, 6 months, 1 year, and then annually through 5 years post index procedure (change from baseline to follow-up)
- NYHA Functional Classification at baseline, 30 days, 3 months, 6 months, 1 year, and then annually through 5 years post index procedure

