Echocardiography images (TTE) obtained at each follow-up visit should be submitted in a timely manner. Throughout the course of the study, the Echocardiography Core Lab may provide feedback to sites regarding quality of images obtained.

During the follow-up period, if a subject requires a cardiac procedure (e.g. MV surgery, permanent LVAD, heart transplant) which may or may not result in explant of the Tendyne device, the subject will remain in the study and continue to be followed.

Every attempt must be made to ensure study subjects do not miss a scheduled follow-up visit. If a subject is unable to complete a visit, the site may attempt to contact them remotely to document their status (e.g., alive) and to administer study questionnaire (KCCQ). This should only be performed in rare instances and the Sponsor should be notified of such instances in advance.

Subjects who do not complete a required follow-up visit will be documented as having a missed visit and a protocol deviation (refer to **Section 12.5 - Deviations from Clinical Investigation Plan**) will be completed. The investigator will keep a record of documented follow-up attempts in the subject's file.

Table 2. Follow-up Schedule and Windows for Study Subjects

| Follow-Up Visit | Window Start Day | Target Day | Window Close Day | Follow up Method |
|---|------------------------------|----------------|------------------|---------------------------|
| Pre-Discharge | Within 72 hours of discharge | Discharge date | N/A | In hospital or Site visit |
| 30 Days (-3 /+14 days) | 27 | 30 | 44 | Site visit |
| 3 Months (± 30 days) | 60 | 90 | 120 | Site visit |
| 6 Months (± 30 days) | 152 | 182 | 212 | Site visit |
| 1 year (± 30 days) | 335 | 365 | 395 | Site visit |
| 2 years (± 30 days) | 701 | 731 | 761 | Site visit |
| 3 years (± 45 days) | 1051 | 1096 | 1506 | Site visit |
| 4 years (± 45 days) | 1416 | 1461 | 1506 | Site visit |
| 5 years (± 45 days) | 1781 | 1826 | 1871 | Site visit |
| Follow-up visit dates are calculated from the date of the index procedure | | | | |

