10.2.9 Handling of Missing Data

Primary analyses will consist of all available data evaluated under ITT principles, referred to in International Conference on Harmonization module E9 (Statistical Principles for Clinical Trials)

as the full analysis set. Consequently, data will only be absent from analyses of study outcomes in the event that they were not available for collection.

In general, missing values in any of the endpoints will not be inputted when summarizing these endpoints using descriptive statistics.

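### 6MWT and KCCQ change is summarised only over tested survivors, with no rule for death or a permanent LVAD, so functional benefit over 5 years may be overstated

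*Combined protocol and SAP*

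**What the plan says.** Section 3.2 makes change from baseline in 6MWT distance and KCCQ score clinical endpoints at 30 days, 3 and 6 months, 1 year, and yearly to 5 years. Section 10.2.7 summarises these variables by number of observations, mean, SD, minimum, maximum and 95% CI, and adds: "Change from baseline will be included using these same descriptive statistics".

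Section 10.2.9 sets the data rule: "Primary analyses will consist of all available data evaluated under ITT principles". It also says that, in general, "missing values in any of the endpoints will not be inputted when summarizing these endpoints using descriptive statistics". Neither section says how a death enters these summaries.

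Section 8.2 deals with later cardiac procedures. Its examples are mitral valve surgery and "permanent LVAD, heart transplant) which may or may not result in explant of the Tendyne device, the subject will remain in the study". No analysis rule is attached to values collected afterwards.

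Patient Success (Section 3.2, years 1 to 5) requires Device Success, return to the pre-procedural setting, a gain of at least one NYHA class, at least 50 m on the 6MWT and at least 10 KCCQ points. Its re-intervention component reads: "No transcatheter or surgical re-interventions for mitral valvular disease (modified from MVARC guidelines". Device Success (Section 3.1) refers to procedural mortality or stroke, placement of the device, unplanned procedures related to the device or access, and continued performance of the device. A late death and an LVAD are not named in either definition.

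**The concern.** An available-case mean at year 3 or 5 describes those who survived and could be tested. If the subjects who leave would have changed less, the mean rises as they leave, and a single-arm study has no comparison group to show how much of the rise is selection. Section 3 sets no pass or fail criterion, so these descriptive tables are the result. Section 2.4.1 lists better symptoms and quality of life first among the potential benefits and says that the findings may shape later protocols.

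The second issue is classification. An LVAD placed for ventricular failure is not a re-intervention for mitral valve disease, and need not be related to the device or access. A recipient who keeps the valve and meets the other criteria would satisfy Patient Success as written.

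**Working it through.** **Figures in the plan.** The plan gives no effect size, SD, mortality or dropout assumption for this study, so there is no functional figure to reproduce. Its only mortality figure in patients with MAC (Section 2.2.2) checks: 19/64 = 29.7%, exact 95% CI 18.9 to 42.4. It is periprocedural death with other valves used off-label. It shows that substantial mortality is conceivable in MAC, and it is not an estimate for this device or for attrition over 5 years.

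**1. Denominator.** Inputs: N = 30 (Section 10.1) and the thresholds in Section 3.2. Assumptions: two thirds of tested subjects improve, and 3 to 12 subjects are dead or untested. Intervals are Clopper-Pearson.

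| Dead or untested | Improved / tested | Improved / all 30 |
|---|---|---|
| 3 | 18/27 = 66.7% | 18/30 = 60.0% (40.6 to 77.3) |
| 9 | 14/21 = 66.7% | 14/30 = 46.7% (28.3 to 65.7) |
| 12 | 12/18 = 66.7% (41.0 to 86.7) | 12/30 = 40.0% (22.7 to 59.4) |

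If the 12 in the last row are 9 deaths and 3 alive but untested, leaving out the 3 gives 12/27 = 44.4% (25.5 to 64.7). The two treatments of untested subjects thus bracket the result at 40.0% to 44.4%. None of this assumes any link between survival and function.

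**2. Shift in the mean.** Suppose functional change has standard deviation SD and latent correlation rho with survival, and a fraction d has died. Then

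shift = rho × SD × φ(z_d) / (1 − d),

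where z_d is the d-quantile of the standard normal. At d = 0.3 the factor is 0.3477/0.7 = 0.497; at d = 0.5 it is 0.3989/0.5 = 0.798. SD, d and rho are all assumptions.

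| Endpoint, assumed SD | d | rho = −0.2 | rho = 0 | rho = 0.2 | rho = 0.4 |
|---|---|---|---|---|---|
| 6MWT, 80 m | 0.3 | −7.9 | 0 | +7.9 | +15.9 |
| 6MWT, 80 m | 0.5 | −12.8 | 0 | +12.8 | +25.5 |
| KCCQ, 20 points | 0.3 | −2.0 | 0 | +2.0 | +4.0 |
| KCCQ, 20 points | 0.5 | −3.2 | 0 | +3.2 | +6.4 |

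The mean is pushed up only if those who die would have done worse (rho > 0). That is plausible in a sick population, but the documents do not show it.

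**3. Values after an LVAD or transplant.** With k such subjects among n tested, each g metres away from what they would otherwise have walked, the mean moves by k × g / n. For k = 2 and n = 15, it moves by 2 × 100/15 = +13.3 m if each is 100 m better, and by 2 × (−50)/15 = −6.7 m if each is 50 m worse. The sign is open.

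**4. Patient Success, case by case.**
- Mitral valve surgery fails the re-intervention component.
- Transplant or explant removes the valve, so Device Success fails on placement and continued performance.
- A permanent LVAD with the valve retained fails nothing by name. One such subject is worth 1/30 = 3.3 percentage points, or 1/15 = 6.7 if 15 are evaluated.
- A late death is not procedural mortality. Section 10.2.7 states no denominator, so under the available-data rule a subject who has died could drop out instead of counting as a failure.

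**The case against.** Much of the attrition would be visible. Section 10.2.7 reports n with every mean and gives descriptive statistics for the components of each composite, so the KCCQ and 6MWD responder counts largely exist at the annual visits. Mortality is reported at 3 and 6 months and yearly to 5 years. Section 10.2.2 tabulates discontinuations by reason, Section 10.2.1 promises subject listings, and Section 10.2.4 adds an as-treated analysis of subjects whose device remains implanted. KCCQ may be collected remotely in rare instances (Section 8.2). The study tests no hypothesis, Section 10.1 leaves further detail to a SAP, and following subjects after later procedures fits the intention-to-treat principle.

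These points stand and limit the weight of the concern. They do not close the gap. The reported n does not separate dead from untested, mortality is never combined with function, and the responder components have no stated denominator. The as-treated set still omits the dead and keeps an LVAD recipient whose valve is in place.

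A reader might go further and infer three things that the documents do not support:
- That benefit is overstated. Neither the direction nor the size follows from the plan, and values after an LVAD or transplant can move the mean either way.
- That a transplant recipient could be a Patient Success. Device Success already rules this out.
- That the 29.7% indicates the attrition to expect. It is periprocedural death with other devices.

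**Conclusion.** The point holds in a limited form. As written, 6MWT and KCCQ change is an available-case summary among tested survivors, with no rule for death, so benefit may be overstated. That an LVAD recipient's later values enter as ordinary data is an inference from Sections 8.2 and 10.2.9 read together; no sentence says so outright.

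The denominator effect is the firm part: 66.7% of those tested against 60.0% down to 40.0% of all 30, given the assumed two-thirds response and 3 to 12 subjects dead or untested. The shift in the mean is conditional: for the 6MWT at 50% deaths it runs from about −13 m to +26 m over rho from −0.2 to 0.4, and it is zero if survival is unrelated to functional change. The Patient Success gap is confined to a permanent LVAD with the valve retained and to late deaths without a stated denominator; the documents give no frequency for the former. For a descriptive study of up to 30 subjects this is a worthwhile, inexpensive improvement.

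**What to change.** Add to Section 10.2.7, for each visit:

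- **(a) Accounting.** The numbers with attempted implant (the set defined in Section 10.2.4), dead, alive but untested, and tested, with the baseline mean of those tested.
- **(b) Responders among all treated.** The proportion of all attempted-implant subjects who are alive with a KCCQ gain of at least 10 points, and likewise with a 6MWD gain of at least 50 m, each with an exact 95% CI. Death counts as not improved. Show alive-untested subjects once as not improved and once excluded, so that no new field for the reason a test was missed is needed. Flag values after a permanent LVAD, transplant or explant, and count them as not improved.
- **(c) Patient Success.** State that the denominator is all attempted-implant subjects due for the visit, that death is a failure, and that a permanent LVAD is a failure. The LVAD rule changes a definition in Section 3.2, so that section and the protocol summary need the same edit.

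Keep the available-case mean and label it as among tested survivors.

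The cost is wording and a few more table rows, with no new visit or measurement. The downside is that the functional figures will look less favourable. Counting death and LVAD as non-response is also a choice of estimand, which is why the survivor mean stays beside it.

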4.2 Number of Subjects to be Registered

This study will enroll male and female subjects who satisfy the inclusion and exclusion criteria and provide written informed consent. This study will register up to 30 subjects at up to 10 investigational sites in the U.S.

Subjects are enrolled in the study upon signing the informed consent form. Subjects are considered registered in the study upon attempt of the implant procedure.

There is no minimum number of subjects to be registered at any site.

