10 STATISTICAL METHODS

10.1 Sample Size Considerations

This is a feasibility study and no formal statistical hypotheses are to be tested for any of the study endpoints. Data collected from this study will provide preliminary device safety and effectiveness data for the use of the Tendyne Mitral Valve System in subjects with mitral regurgitation and mitral annular calcification. Descriptive statistics will be reported for the study data primarily. Inferential statistical analysis will be conducted in an exploratory manner. The sample size for this study is planned to be up to 30 at up to 10 investigational sites.

Statistical methods for the study are outlined below. Additional details will be provided in a Statistical Analysis Plan (SAP).

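### The stand-alone NYHA endpoint has no per-subject summary before year 1, so selective loss of class III/IV subjects can make its visit percentages look like improvement

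*Combined protocol and SAP*

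**What the plan says.** Section 3.2 of the protocol defines the 6MWT and KCCQ endpoints with a closing phrase that makes them within-subject: "years post index procedure (change from baseline to follow-up". The NYHA endpoint in the same list has no such phrase: "NYHA Functional Classification at baseline, 30 days, 3 months, 6 months, 1 year, and then annually through 5 years post index procedure". The summary at the front of the protocol draws the same distinction.

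Section 10.2.7 follows this through. For continuous variables it adds: "Change from baseline will be included using these same descriptive statistics". For NYHA it says only: "For categorical variables such as mortality and NYHA classification, results will be summarized with subject counts and percentages/rates, and with 95% confidence intervals".

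Section 10.2.9 states that "missing values in any of the endpoints will not be inputted when summarizing these endpoints using descriptive statistics". No section gives deceased subjects a category in the NYHA summary.

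A paired NYHA measure does appear inside Patient Success in section 3.2: "Improvement from baseline symptoms (NYHA improvement by ≥ 1 Functional Classification); and". Patient Success is evaluated at 1, 2, 3, 4 and 5 years only. Section 10.2.7 promises descriptive statistics for the components of each composite, so this component will be reported at those visits.

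**The concern.** Percentages by visit compare groups of people, not people with themselves. The text describes no NYHA table columns. Under the available-data rule, though, the natural reading is that the baseline percentages cover everyone treated and later percentages cover only those seen. If the subjects who drop out of the table were mostly in class III or IV, the remaining mix looks better with no change in any individual.

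Three features make this more than a formality.

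- The visits with no per-subject NYHA result (30 days, 3 months, 6 months) are the ones that follow most closely on procedural deaths.
- Under section 8.2, remote contact for a missed visit covers vital status and the KCCQ. NYHA is not named, so a subject too ill to attend can stay in the KCCQ summary and leave the NYHA one.
- The study has a single arm, so no control group would reveal the effect. Section 2.4.1 already cites post-procedure NYHA improvement in compassionate-use patients as part of the rationale, and says the results may shape later protocols.

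**Working it through.** The plan states no NYHA figure, power or effect size to reproduce: section 4.2 says "This study will register up to 30 subjects at up to 10 investigational sites in the U.S" and section 10.1 says "no formal statistical hypotheses are to be tested for any of the study endpoints". The check is therefore direct arithmetic on stated assumptions.

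**Inputs from the documents.** N = 30, the maximum. Entry requires class II or worse (section 5.2.2), so class I is 0% at baseline. Missing values are not imputed (section 10.2.9).

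**Assumptions, not in the documents.** The baseline split is 10 in class II and 20 in class III/IV. Nine subjects die. No survivor changes class. The nine deaths only set a scale: the registry of other transcatheter valves in MAC cited in section 2.2.2 had 19/64 = 29.7% periprocedural deaths, and 30 × 19/64 = 8.9. This is not a forecast for this device.

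**Formula.** Let r be the risk of death in class III/IV relative to class II, and d the number of deaths. Expected deaths in III/IV are d × 20r / (20r + 10), and the rest are in class II. Visit share in class I/II = (10 − class II deaths) / (30 − d). The baseline share is 10/30 = 33.3%.

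| Where the 9 deaths fall | Deaths in III/IV | Class II survivors | Visit share of I/II |
|---|---|---|---|
| All in class II | 0 | 1 | 1/21 = 4.8% |
| Proportional (r = 1) | 6 | 7 | 7/21 = 33.3% |
| r = 2 | 9 × 40/50 = 7.2 | 8.2 | 8.2/21 = 39.0% |
| r = 3 | 9 × 60/70 = 7.71 | 8.71 | 8.71/21 = 41.5% |
| All in III/IV | 9 | 10 | 10/21 = 47.6% |

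**Range over other splits and death counts**, all deaths in III/IV (the upper extreme):

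| Baseline III/IV | Baseline I/II share | 3 deaths | 6 deaths | 9 deaths | 12 deaths |
|---|---|---|---|---|---|
| 15/30 | 50.0% | 55.6% | 62.5% | 71.4% | 83.3% |
| 20/30 | 33.3% | 37.0% | 41.7% | 47.6% | 55.6% |
| 24/30 | 20.0% | 22.2% | 25.0% | 28.6% | 33.3% |

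**The same data, paired.** In the extreme case of the first table, a shift table over all 30 reads: improved 0, unchanged 21, worse 0, dead 9, alive but not assessed 0. Improvement by at least one class is 0/21 among survivors (exact 95% CI 0 to 16.1%) and 0/30 among all treated (0 to 11.6%). The survivors' own baseline share in class I/II is 10/21 = 47.6%, the same as at the visit, so printing it alongside removes the apparent gain.

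Missed visits act in the same way as deaths, since both leave the denominator.

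**The case against.** The case for leaving the text alone has several parts.

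- *A paired NYHA result is already planned.* This is true at five of the eight follow-up visits, so a reader who inferred that NYHA is analysed only in unpaired form would be wrong. The component is yes/no, however. It does not separate unchanged from worse, has no stated place for deaths, and does not exist before year 1.
- *Section 10.2.1 allows cross tabulations and promises subject listings, and section 10.1 defers detail to a SAP.* The present wording permits a shift table, and listings would let a reader rebuild one. Neither commits the sponsor to producing it, and no separate SAP text is among the documents reviewed.
- *The output partly exposes the problem.* Counts accompany percentages, so 10 of 30 followed by 10 of 21 shows no gain in numbers. Mortality is reported separately. Class I cannot rise from 0% through deaths, so anyone in class I at follow-up has truly improved. All this stands, but a mortality count does not show which baseline classes were lost.
- *The shift is small against the sampling error.* Even in the extreme case, the exact 95% intervals overlap widely: 17.3 to 52.8% for 10/30 and 25.7 to 70.2% for 10/21. That is so, but those intervals do not account for selective loss.
- *6MWT and KCCQ also lose the dead.* They do, but a paired change cannot show improvement when nobody improved.

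**Conclusion.** The point holds as a gap in reporting. The stand-alone NYHA endpoint is planned as counts and percentages by visit. No per-subject summary is specified at 30 days, 3 months or 6 months, and worsening is not summarised at any visit. The visit percentages can then suggest improvement that no survivor experienced.

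The size is conditional. With 10 of 30 in class II and 9 deaths, the apparent gain in class I/II is 0 points if deaths are proportional to class, 5.7 points (39.0 − 33.3) at a relative risk of 2, 8.2 points (41.5 − 33.3) at 3, and 14.3 points if every death is in III/IV. It turns negative if deaths fall in class II. The baseline split, the number of deaths and their distribution by class are all assumed.

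A reader might infer that deaths will necessarily appear as functional improvement, or that a study conclusion hangs on this table. The documents support neither. The shift requires disproportionate loss of class III/IV subjects. NYHA is one of seven clinical endpoints; the primary endpoint is 30-day safety. Section 3 sets no pass or fail criteria, and no hypothesis is tested. The consequence is a table open to misreading, not a wrong decision.

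**What to change.** In sections 3.2 and 10.2.7, and in the SAP when written, add a baseline-by-visit NYHA shift table at every follow-up visit. Report the number and percentage improved by at least one class, unchanged, worse, dead, and alive but not assessed. Use all subjects with an attempted implant as denominator, which matches the primary analysis sample in section 10.2.4. If visit percentages are kept, print beside them the baseline percentages of the same subjects.

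NYHA is already collected at baseline and at each visit from 30 days on (Appendix III), so no new data are needed. The cost is wording, a little more table work, and possibly less favourable figures. Other layouts could serve; what matters is that each subject is compared with his or her own baseline and that losses are visible in the same table.
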